Authorship policies will conform to the International Committee of Medical Journal Editors (ICMJE) criteria. (International Committee of Medical Journal Editors, 2015) The ICMJE recommends that authorship be based on the following 4 criteria: (1) substantial contributions to the conception or design of the work; or the acquisition, analysis, or interpretation of data for the work; AND (2) drafting the work or revising it critically for important intellectual content; AND (3) final approval of the version to be published, AND (4) agreement to be accountable for all aspects of the work in ensuring that questions related to the accuracy or integrity of any part of the work are appropriately investigated and resolved. All authors should meet all 4 criteria, and any Investigator meeting criterion 1 is to be given the opportunity to meet criteria 2 and 3.

The IDE Sponsor will, at a minimum, have the right to advance review publications and presentations before dissemination for the sole purpose of removing Sponsor's confidential information.

The individual clinical centers will not publish efficacy or safety data if those data were collected as part of a multicenter study. Main results of the trial will be published before other data from the study. Submission of data and analyses to the FDA may be done at any time after the database is quality checked and finalized; regulatory submissions will not be delayed pending publication.

DATA DISTRIBUTION AND USE

The anonymized primary database will be distributed to the IDE Sponsor and to the State of Ohio according to the terms of the Request for Proposal (State of Ohio (2021 RFP Number SRC0000002472, Index Number DMH009).

The linkage table of names with participant identifiers will be unavailable to the Investigators after the locked Study database is transmitted to the IDE Sponsor and the representative of the State of Ohio. Linkage tables received from the sites will be transmitted by the Study PI to the IDE Sponsor.

REFERENCES

- Abelson, J. L., Curtis, G. C., Sagher, O., Albucher, R. C., Harrigan, M., Taylor, S. F., . . . Giordani, B. (2005). Deep brain stimulation for refractory obsessive-compulsive disorder. *Biol Psychiatry*, 57(5), 510-516.
- Achard S, D.-M. C. (2012). Hubs of brain functional networks are radically reorganized in comatose patients. *Proceedings of the National Academy of Sciences, USA*, (pp. 20868-20613).

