	 Sample size selected to allow detection of safety concerns in the
	broad PTSD population to be recruited for Stage 2
	 A maximum of 400 individuals will be screened in order to
	achieve the recruitment goal
	Stage 2
	• Total recruitment goal:
	\circ 120
	\circ 108 completers (90%)
	• Assignment ratio =1:1 for Active eTMS vs. Sham eTMS

Statistical Methods (Stage 1)	 Primary outcome time point = F1 Planned estimated effect size +0.8 SD_{difference}, for a difference in Active eTMS versus Sham eTMS group mean pre-post PCL-5 scores = 15, with pooled SD_{difference} = 18.68 Type 1 error = 0.05 (2-sided) Statistical power = 98.5 % Method of calculation – Sample size and power for given detectable difference between two mean difference scores using Student's t-test according to method of Dupont & Plummer Design variable is change in PCL-5 between BL and F1. Mean in a first responder population = 38.73 (SD = 18.68) (Morrison, Su, Keck, & Beidel, 2021) Clinically important difference (MCID) = 10 - 20 Adverse events characterized by: Frequency Relatedness Severity Type DSMB to review and make recommendations regarding: Whether to proceed to Stage 2 Protocol changes for Stage 2
Statistical Methods (Stage 2)	 Intention to Treat (ITT) population to analyze the primary outcome, with secondary analyses using Per Protocol (PP) population Primary outcome tested by linear regression of change score between Baseline (BL) and end of treatment (F1) at 5% Type 1 error rate Multiple linear regression imputation of missing data assuming missing at random (MAR), and best-case/worst-case sensitivity analyses Poolability of data from all sites tested Exploratory outcomes tested, as appropriate, according to level of data (e.g., categorical, ratio), number of time points at which measured, and fulfillment of statistical assumptions DSMB monitors emerging safety, efficacy, recruitment and performance data DSMB to recommend continuation/termination One interim analysis of efficacy data after approximately 50% completers Haybittle-Peto alpha-spending and stopping rule

STUDY SYNOPSIS	2
TABLE OF CONTENTS	. 10
LIST OF ABBREVIATIONS	. 13
INTRODUCTION AND RATIONALE	. 16
Post-Traumatic Stress Disorder	. 16
Treatment for Posttraumatic Stress (PTSD)	. 19
Repetitive Transcranial Magnetic Stimulation (rTMS)	. 20
Electroencephalogram (EEG) personalized Transcranial Magnetic Stimulation (eTMS)	. 25
Preliminary Data	. 26
STUDY OBJECTIVE	. 27
STUDY DESIGN	. 28
Stage 1	. 28
Stage 2	. 28

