eTMS-PTSD-001 comprises two stages. Stage 1 is an open-label safety pilot study with a recruitment goal of 30 subjects, with 26 completers. Stage 1 is intended to evaluate the safety aspects of eTMS in the target population. A maximum of 400 individuals will be screened in order to achieve the recruitment goal. The total number of days from the first participant enrolled to the last enrolled participant treated will be approximately 7 months. Following Stage 1, a recommendation will be made by the DSMB as to whether the safety results warrant proceeding to Stage 2. Stage 2 is a prospective randomized, double-blind, sham-controlled trial of eTMS, with an open-label period for sham-assigned participants following the randomized portion. The recruitment goal for Stage 2 is 140 subjects, with 126 completers (90%). Participants will be either Veterans or First Responders (e.g., emergency medical service provider, firefighter, or any other emergency response personnel), between 22-65 years of age. Participants may be male or female of any racial/ethnic background who meet the eligibility criteria. Participants will be recruited from the general public, and from veterans and first responder organizations.

Stage 1

Stage 1 consists of an open-label safety pilot study. The primary outcome for Stage 1 will be the incidence, severity, relatedness, type, subsequent treatment/intervention required, and resolution status of adverse events during the study. A total of 30 participants will be recruited for this stage.

Following Stage 1 completion, the Data and Safety Monitoring Board (DSMB) will meet to recommend whether to continue to Stage 2. Upon approval from the DSMB, a supplementary IDE will be submitted to FDA for approval to proceed to Stage 2.

Stage 2

Stage 2 is intended to establish the efficacy and safety of eTMS for treatment of PTSD in the target population. The primary outcome of the trial for Stage 2 is reduction in symptoms of PTSD as calculated by arithmetic reduction in the PCL-5 assessment. A total of 140 participants will be randomized for this Stage.

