All subjects who finish BL assessments and meet inclusion/exclusion criteria will be randomized into one of two groups, "Active eTMS" and "Sham eTMS", in a 1:1 ratio, stratified by clinic. Stage 2 will consist of a randomized period and an open-label period. During the randomized period, the Active eTMS group will receive Active eTMS and the Sham eTMS group will receive Sham eTMS twice per day, with 20 total treatments delivered in a 2 or 3-week period. Following the randomized period of the study, all Sham eTMS subjects will have the option of participating in the open-label portion of the study. Those who choose to participate in open-label treatment will receive 20 Active eTMS sessions, twice per day, which must be completed in a period of 21 calendar days.

All groups will undergo an assessment of symptoms at baseline, before Week 6 (F1), and then again at the end of Week 10 (F2). The primary efficacy endpoint, and outcome time point, is Wave Neuroscience, Inc. Protocol eTMS-PTSD Rev 1.1 11 January 2024 PAGE 28 change in Post-Traumatic Stress Disorder symptoms between the Baseline (BL) and the first follow-up (F1). The primary efficacy outcome will be measured using the PCL-5. Safety outcomes will be measured by recording adverse events, incidence and type.

PARTICIPANT POPULATION

The enrollment goal for the combined two stages of the study is 170 participants of any gender or ethnic background, age 22-65 years, with Post-Traumatic Stress Disorder. Thirty (30) participants will be part of Stage 1 and be provided with open-label treatment to evaluate safety of eTMS in this population. 140 participants will be part of Stage 2, randomized to either active or sham eTMS, in a 1:1 allocation ratio, stratified by recruitment site. Participants randomized to sham eTMS in Stage 2 will receive an additional series of open-label active eTMS following the randomized portion of Stage 2.

Inclusion Criteria

Participants must meet all following inclusion criteria to qualify for enrollment into the study:

- 1. Willing and able to consent to participate in the study via signed Informed Consent
- 2. Age 22 65 years
- 3. Provisional diagnosis of PTSD according to Veterans Administration PCL-5 rubric fulfillment AND cutpoint score of 31 or above
- 4. Positive identification as either a Veteran, or First Responder (e.g., emergency medical service provider, firefighter, or any other emergency response personnel)

Exclusion Criteria

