
Stage 2

Stage 2 of the trial is intended to investigate efficacy and safety of the procedure in the target population. The primary efficacy outcome is a measure of PTSD symptom severity. PTSD symptom reduction will be calculated as the arithmetic reduction in PCL-5 scores between BL and F1. See the above Data Collection section for a description of this assessment.

Safety will be characterized by adverse event incidence, relatedness, severity, type, subsequent treatment/intervention required, and resolution status.

SAMPLE SIZE CONSIDERATIONS FOR STAGE 1

A convenience sample size of thirty (30) will be treated in the safety pilot stage in order to detect common adverse effects or safety concerns.

SAMPLE SIZE CONSIDERATIONS FOR STAGE 2

Sample size assumptions:

[figure not shown]
- Design variable is change in PCL-5 between BL and F1.
 - Mean in first responders = 38.73 (SD = 18.68) (Morrison, Su, Keck, & Beidel, 2021)
 - Primary outcome clinically important difference = 15(10-20) (U.S. Department of Veterans Affairs, 2022)
- Planned estimated effect size +0.8 SD_{difference}, for a difference in Active eTMS versus Sham eTMS group mean pre-post PCL-5 scores = 15, with pooled SD_{difference} = 18.68
- Assignment ratio =1:1 for Active eTMS vs. Sham eTMS
- 10% loss to followup

- Type 1 error = 0.05 (2-sided)
- Statistical power = .985
- Method of calculation Sample size and power for given detectable difference between two mean difference scores using Student's t-test according to method of Dupont & Plummer

Sample size requirements:

- Total completers: 108 (90% 54 per group) See Figure 2 below
- Total to be randomized:120 (60 per group)

FIGURE 2: Primary efficacy outcome, PCL-5. Statistical power by number of completers per treatment group for Type 1 error 0.05 (.985) and 0.01 (.938)

DATA AND SAFETY MONITORING BOARD

A Data and Safety Monitoring Board (DSMB) comprised of at least 3 **independent** subject matter, medical, clinical trial methods, and biostatistics experts will be constituted to review the protocol, recruitment progress, site performance, study conduct, and safety data. The Board will request analyses, and will make recommendations regarding study continuation, amendment, or termination, as well as the advisability of adding up to 3 additional research sites.

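### Stage 2 has two conflicting sizes in the same revision, 120 randomised (108 completers) and 140 randomised (126 completers), and nothing says which governs

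*Combined protocol and SAP*

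**What the plan says.** **140 randomised, 126 completers.** The opening paragraph of Study Design says "The recruitment goal for Stage 2 is 140 subjects, with 126 completers (90"%). Its Stage 2 subsection adds "A total of 140 participants will be randomized for this Stage". Participant Population says "The enrollment goal for the combined two stages of the study is 170 participants", made up of 30 in Stage 1 and the rest in Stage 2: "140 participants will be part of Stage 2, randomized to either active or sham eTMS".

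**120 randomised, 108 completers.** The synopsis, under Sample Size Justification, gives a Stage 2 recruitment goal of 120 with "108 completers (90"%) and "Statistical power = 98.5"%. The sample size section for Stage 2 repeats this as requirements: "Total completers: 108 (90% 54 per group") and "Total to be randomized:120 (60 per group"). The Figure 2 caption gives power of .985 at alpha 0.05 and .938 at alpha 0.01.

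**What depends on the size.** The Data and Safety Monitoring Board section times the single interim analysis at about half of the expected completers. It sets the efficacy boundary at two-sided p ≤ 0.001 and the final criterion at p ≤ 0.049. It describes futility through conditional power at the end of the study, assuming a difference of 15, with 20% as an example threshold. It gives no absolute count for the interim look or for the end of the study.

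**The concern.** The planned size is an operating instruction, and these sections cannot both be followed. 140 is not described as a maximum, a re-estimated size or an amended size, and there is no order of precedence. It does not look like a typing slip, because 140 is repeated and carries its own consistent completer count and overall total.

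Four quantities take two values: the enrolment stop (120 or 140), the combined total (150 or 170), the interim count (about 54 or 63 completers) and the final number used for conditional power (108 or 126). If the larger figure is followed, the last 20 participants, half of them on sham, are randomised without a supporting calculation.

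**Working it through.** **Inputs.** From the Stage 2 sample size section: difference 15, SD of change 18.68, two-sided alpha 0.05, 1:1 allocation, 10% loss, Student's t-test. From the DSMB section: interim at about 50% of completers, boundaries 0.001 and 0.049, conditional power assuming 15, example threshold 20%.

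**1. Each set is coherent in itself.**
- 108 / 0.9 = 120, and 30 + 120 = 150 combined (150 is not stated anywhere).
- 126 / 0.9 = 140, and 30 + 140 = 170 combined (as stated).

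**2. Which set the stated power belongs to.** For n completers per group, the noncentrality parameter is 15 / (18.68 × √(2/n)) with 2n − 2 degrees of freedom. Power is the noncentral t probability beyond the two-sided critical value. At n = 54 the noncentrality is 4.17; at n = 63 it is 4.51.

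| Completers per group | Power, alpha 0.05 | Power, alpha 0.01 |
|---|---|---|
| Protocol states | .985 | .938 |
| 53 | 0.984 | 0.932 |
| **54 (108 total)** | **0.985** | **0.937** |
| 55 | 0.987 | 0.942 |
| 63 (126 total) | 0.994 | 0.969 |

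The plan's figures reproduce at 54 per group. The values for 63 per group appear nowhere in the protocol.

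**3. Type I error.** Under a bivariate normal model with one look at 0.001 and a final test at 0.049, overall two-sided error is 0.0492 for both 54/108 and 63/126 (interim/final completers).

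**4. Futility guide, one size used throughout.** Let n1 and n be the per-group numbers at interim and end, t = n1/n, and z1 = observed difference / (18.68 × √(2/n1)). Define B = z1√t + (1 − t) × 15 / (18.68 × √(2/n)). Conditional power is then 1 − Φ((1.969 − B) / √(1 − t)). A positive difference favours active. Completers are taken as the unit of information at both times, which is an assumption.

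Example, 54/108 with an observed −7: z1 = −1.377 and t = 0.5, so B = −0.974 + 0.5 × 4.173 = 1.113. Conditional power = 1 − Φ(0.856 / 0.707) = 11.3%.

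| | 54/108 | 63/126 |
|---|---|---|
| Observed difference at which conditional power is 20% | −5.1 | −5.9 |
| Chance of falling below it, no true effect | 15.7% | 10.7% |
| Chance of falling below it, true difference 15 | 0.004% | 0.0005% |
| Conditional power at an observed −7 | 11.3% | 13.9% |

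**5. Efficacy look, one size used throughout.** With an unadjusted t-test and 27 or 31.5 per group, p ≤ 0.001 needs an observed difference of 17.7 or 16.3. If 15 is true, the chance of reaching it is 31% or 40%.

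**6. Worst case: interim timing from one section, final size from the other.** The information fraction becomes 54/126 = 0.43 or 63/108 = 0.58, and the 20% point moves to −9.7 or −1.9. An observed −7 at 54 completers gives conditional power of 11% if the final number is 108 and 35% if it is 126, on opposite sides of 20%. Type I error stays near 0.049 (0.0493 and 0.0491).

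**The case against.** The strongest reply is that the choice of size hardly affects inference. Under the planning assumptions power exceeds 98% with either size, type I error is unchanged, and the estimand, test and analysis population do not depend on it. The efficacy rule is fully specified as a p-value, so the figures in step 5 only describe two valid designs. The futility guide is permissive, 20% is an example, and other endpoints are weighed first. Interim timing is itself approximate. Nothing suggests that the DSMB would mix the two sections. All of this stands, and the concern does not rest on inferential damage.

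A second point is that the dedicated sample size section agrees with the synopsis and holds the only power calculation, so 120/108 is the justified size. That is good evidence of which size the calculation supports. It is not a rule of precedence, and 140 is written as the number to be randomised.

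A third is that the primary analysis is intention-to-treat with missing F1 scores imputed, so the nominal final sample would be 120 or 140 rather than 108 or 126. This is fair. Using completers for the final information is an approximation, chosen because the interim is counted in completers. The DSMB section should state the number it means. The two sizes remain in conflict on either basis.

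Finally, Stage 2 cannot begin until the DSMB has reviewed Stage 1 and a supplementary IDE has gone to FDA. That provides a point at which to make the correction; it does not make it.

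**Conclusion.** The concern holds. Rev 1.1 gives Stage 2 two sizes that differ by 20 randomised participants and 18 completers, with a combined total of 150 or 170, and nothing resolves them. The stated power fits 120/108 only; 140/126 has no calculation behind it.

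If one size is used consistently, the statistical consequence is modest: power 0.985 against 0.994, type I error about 0.049, and a futility cut-off of −5.1 against −5.9. Readings diverge widely only if the two sections are mixed, which is a worst case and not an expected course.

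The correction is required before Stage 2 because the enrolment stop, the interim trigger and the conditional power denominator all come from this number. The figures assume a difference of 15 and an SD of 18.68. The conditional power results also assume a normal approximation, completers as the unit of information, and a true difference of 15 for the data still to come. The planned baseline-adjusted regression may have a smaller residual SD than the unadjusted change score.

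**What to change.** State one Stage 2 size in every section before Stage 2 starts. The supplementary IDE submission is a natural place to do it.

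- **If 120 is intended:** in Study Design and Participant Population, change 140 to 120, 126 to 108 and 170 to 150. This is wording only. The existing power calculation and Figure 2 stand.
- **If 140 is intended:** change the sizes in the synopsis and the Stage 2 sample size section to 140 randomised and 126 completers (70 and 63 per group). Restate power as 0.994, and the Figure 2 values as 0.994 at alpha 0.05 and 0.969 at alpha 0.01. This randomises 20 more participants (10 per group) than the present calculation supports, so a reason should be given.

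In either case, write the resulting counts into the DSMB section: the interim at about 54 or about 63 completers, and the final number for conditional power as 108 or 126 completers, saying that completers are the unit used.
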